1 INTRODUCTION

1.1 STUDY BACKGROUND

Stress urinary incontinence often leads to subjects limiting their participation in social activities, which in turn has a subsequent impact on a person's quality of life. While some seek surgical intervention, physical therapy is seen as the first treatment option in this often under-reported condition. The purpose of this study is to conduct a pivotal study comparing the Vital Compact device (fourth generation device) to an FDA 510(k) approved predicate device (itouch Sure Pelvic Floor Exerciser).

1.2 STUDY OBJECTIVES

The primary objective of this clinical study is to evaluate and compare the safety and performance profile of the Vital Compact device (delivering electrical stimulation through external electrodes) and the itouch Sure Pelvic Floor Exerciser (delivering electrical stimulation through an internal vaginal probe) for the treatment of stress urinary incontinence following a 12-week treatment program.

1.3 STUDY DESIGN

This is a prospective, randomized, controlled, single-blind, multi-site clinical study to be conducted in the United States of America (USA) employing Neuromuscular Electrical Stimulation (NMES) to stimulate the pelvic floor muscles of women suffering from stress urinary incontinence.

Approximately one-hundred and eighty (180) female subjects diagnosed with stress urinary incontinence will be enrolled in this study. All subjects who are considered eligible to participate in the clinical study and give consent will be randomised to complete either a 12-week treatment programme with the Vital Compact device or a 12-week treatment programme with the itouch Sure Pelvic Floor Exerciser. The 12-week treatment programme will be completed by the subjects at home with treatment with the device in accordance with the device Instructions for Use. Subjects randomized to the Vital Compact device will be instructed to use the device at home once per day, in a therapeutic position, for five days each week with two rest days taken within a 7 day week period, for the 12-week period; each treatment cycle is fixed at 30 minutes and the device will alert the subject when the cycle is completed. Subjects randomized to the itouch Sure Pelvic Floor Exerciser will be instructed to use the device at home once per day for the 12-week period; each treatment cycle is fixed at 20 minutes and the device will alert the subject when the cycle is completed.

Subjects included in the clinical study will be evaluated at screening, on enrolment into the study (baseline) and during the 12-week treatment programme at 4 and 12 weeks. A telephone call will be made at 1 week to check on the subject's progress. In addition, subjects will be evaluated at 26 weeks following their commencement of the treatment.

1.4 SAMPLE SIZE AND POWER

Sample size calculations were performed using the NQuery Advisor® version 5.0, under a two group test of proportions.

Research suggests that the response rates for Vital Compact and itouch Sure at 12 weeks will be 71% and 46%, respectively (itouch success rate based on Sand, 1995).

The sample size calculation is based on the assumption that the itouch Sure Pelvic Floor Exerciser success rate is 52% and the Vital Control success rate is 71%. A sample size of 87 subjects per group will provide 90% power using a one-sided Type I error rate of 0.025, and a non-inferiority margin of 5%. A randomization allocation of 1:1 was also assumed. For practical reasons, the sample size has been increased to a recruitment of 180 subjects (90 subjects per treatment group).

1.5 STUDY POPULATION

1.5.1 MAIN INCLUSION CRITERIA

Female subjects between the ages of 18 and 65 who have been clinically diagnosed with stress urinary incontinence and have failed to improve their condition using Kegel exercises.

1.5.2 MAIN EXCLUSION CRITERIA

Subjects with medical, physical, or neurological conditions that would compromise their participation or make them unable to perform the study procedures.

1.6 STATISTICAL ANALYSIS PLAN (SAP)

1.6.1 SAP OBJECTIVES

The objective of this SAP is to describe the statistical analyses to be carried out under BMR-13-1001.

1.6.2 GENERAL PRINCIPLES

Data will be summarized using descriptive statistics. For continuous measures, this will include number (N), mean, standard deviation, median, and range (minimum and maximum). For categorical measures, counts and percentages will be provided. Data will be summarized separately for each randomized arm under the principles of intent to treat, unless otherwise noted. All statistical tests will be conducted at $\alpha = 0.05$, two-sided significance level, unless otherwise stated. The day of randomization is considered as Day 1 and the day prior to randomization is Day -1. Summaries will be based on the database visits, regardless of the relative day of the visit; early termination visits are to be collected as Week 12 and all follow-up assessments are collected as Week 26.

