8.11.1 Early Termination

If a subject starts treatment discontinues before completing all study visits, she is to be asked to return to the clinic to complete a Visit 4 visit as an early termination visit (if prior to that visit) or a Visit 5 visit (if after Visit 4 has taken place).

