8.11.3 Timing of Visit Assessments (+/- 7 days)

Patients included in the clinical study will return for follow-up visits at 4 weeks (Visit 3) and 12 weeks (Visit 4) during the 12-week treatment programme.

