10.3.4 Analysis Methods

For the primary analysis variable (proportion of patients who respond at Week 12) the difference in the proportions of responders and a 95% CI of the difference in proportion of responders will be calculated using the normal approximation to the binomial distribution. The ITT population will serve as the primary analysis population, with PP population analyses serving as supportive. For the ITT analysis, if a subject does not complete the 12 week assessment, their outcome will be imputed using multiple imputations. Non-inferiority will be claimed if the lower limit of the 95% CI is greater than -5%.

The total number of successes in each study arm will be summarized, along with the corresponding proportions and 95% CIs. The difference between proportions will also be summarized with its corresponding 95% CI.

Sensitivity analyses will be performed to assess the impact of missing data on the primary endpoint results. These analyses will be based on the ITT population. A last observation

carried forward (LOCF) method will be used to account for all missing data. A tipping point analysis will also be performed (Campbell et al., 2011 and Yan X. et al., 2009).

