2.3.2.1 PRIMARY ENDPOINT ANALYSIS

To test these hypotheses, the difference in the proportions of responders and a 95% Confidence Interval (CI) of the difference in proportion of responders will be calculated using the normal approximation to the binomial distribution. Non-inferiority will be claimed if the lower limit of

the 95% CI is greater than -5%. Furthermore, superiority will be claimed if the lower limit of the 95% CI is greater than 0%. The p-value for superiority will also be reported, based on a Chi-Square test. The total number of successes in each study arm will be summarized, along with the corresponding proportions and exact 95% CIs.

The ITT population will serve as the primary analysis population. For this analysis, if a subject does not complete the 12 week assessment, their outcome will be imputed using multiple imputations (Schafer, 1997). The multiple imputation methodology will be implemented as follows:

1. Ten imputed datasets will be generated to impute missing urine leakage using the below SAS code. Only the imputed values at Week 12 will be retained.

```
Proc MI NIMPUTE=10 SEED=20150930 MIN=0 0 0 MAX= . . .;  
  var base w4 w12;  
  fcs reg(base) reg(w4) reg(w12);  
run;
```

2. The ten imputed datasets will be analyzed separately. Using the methodology described above, the Week 12 urine leakage will be compared against the baseline weights to classify subject responders.
3. The proportion of responders in each treatment group, along with the associated standard error, will be calculated for each of the ten imputed datasets. The individual proportion estimates and standard errors will be pooled by treatment using the SAS code below.

```
Proc MIANALYZE;  
  modeleffects prop;  
  stderr se_prop;  
  by trt;  
run;
```

4. The difference in the proportions of responders and the standard error of the difference will be calculated for each of the ten imputed datasets. The individual estimates of the difference in proportions, as well as the associated standard errors of the differences, will be pooled using the SAS code below.

```
Proc MIANALYZE;  
  modeleffects prop_diff;  
  stderr se_diff;  
run;
```

A supportive analysis will also be conducted using similar methodology in the PP population.

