2.3.2.2 SENSITIVITY ANALYSES

Sensitivity analyses will be performed to assess the impact of missing data on the primary endpoint results. These analyses will be conducted on the ITT population. Two techniques will be employed: the Last Observation Carried Forward (LOCF) method and the Tipping Point analysis (Yan, 2009).

The LOCF method will impute any missing Week 12 urine leakage with the most recent value collected. The difference in the proportions of responders and a 95% CI of the difference in proportion of responders will be calculated using the normal approximation to the binomial distribution. The p-value for superiority will also be reported, based on a Chi-Square test. The total number of successes in each study arm will be summarized, along with the corresponding proportions and exact 95% CIs.

The Tipping Point analysis will be performed directly on the binary endpoint of subject responder (i.e. whether or not the subject achieved ‘significant improvement’). It will be implemented as follows:

1. Determine the number of missing values in each treatment arm:
Let n_{1m} = number of missing values in the Vital Compact group
Let n_{2m} = number of missing values in the itouch Sure Pelvic Floor Exerciser group
2. Impute the missing data in each group so that all possible combinations of responder/non-responder are considered. Starting at 0 and ending at n_{1m} , the responder rate in the Vital Compact group will be changed by adding 1 responder at a time. Meanwhile, the responder rate in the itouch Sure Pelvic Floor Exerciser group will also be changed by adding 1 responder at a time, starting at 0 and ending at n_{2m} . The difference in the proportions of responders and a 95% CI of the difference will be calculated for each case.
The algorithm is as follows:
 - a. Let s_1 represent the number of responders within the group of missing Vital Compact data.
Let s_2 represent the number of responders within the group of missing itouch Sure Pelvic Floor Exerciser group data.
 - b. Set $s_1 = 0$
 - c. Set $s_2 = 0$
 - d. Calculate the difference of proportions and associated 95% confidence interval.
 - e. $s_2 = s_2 + 1$, where $s_2 \leq n_{2m}$
 - f. Repeat steps (d) to (e).
 - g. $s_1 = s_1 + 1$, where $s_1 \leq n_{1m}$. Continue to steps (c) to (f).
3. Present the lower 95% confidence limit for each possible missing data combination.

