3.7.2 DEVICE USE – PERCENT OF ACTUAL USE

The percentage of actual use (through the usage period) is calculated as

$$\text{Actual Use (\%)} = \frac{\text{number of sessions used}}{\text{number of sessions expected}} * 100$$

where the number of sessions used is obtained from the daily record and the number of sessions expected is based on the relative day of the Week 12 visit. [For itouch Sure subjects, the number of sessions expected is the relative day of the visit minus 1; for Vital Compact subjects, it is the truncated value of $5/7 * (\text{relative day} - 1)$].

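### The primary-endpoint imputation code ignores treatment arm, and no planned missing-data analysis varies an early-termination reading stored as Week 12

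*SAP*

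**What the plan says.** **Imputation.** Protocol 10.3.4 states that "if a subject does not complete the 12 week assessment, their outcome will be imputed using multiple imputations", and SAP 2.3.2.1 repeats this. The SAP's PROC MI step has the variable list "var base w4 w12" and regression models for those three variables. Treatment does not appear in the step, as a variable or as a BY group. The later PROC MIANALYZE step that pools each arm's proportion is run by treatment.

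**Early termination.** Protocol 8.11.1 says of a subject who stops before Visit 4 that "she is to be asked to return to the clinic to complete a Visit 4 visit as an early termination visit". SAP 1.6.2 carries this into the data: "early termination visits are to be collected as Week 12 and all follow-up assessments are collected as Week 26". The same paragraph bases summaries on the nominal database visit and ignores its relative day. Protocol 8.11.3 gives Visits 3 and 4 a window of 7 days either side.

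**Missing-data checks.** In SAP 2.3.2.2, "The LOCF method will impute any missing Week 12 urine leakage with the most recent value collected". The tipping-point analysis begins with "Determine the number of missing values in each treatment arm" and runs over those counts, n1m and n2m.

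**The concern.** Non-inferiority is judged against a 5-point margin, so the handling of subjects without a true Week 12 value matters.

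The analysis compares arms, but the imputation model assumes that, given baseline and Week 4 leakage, the arm tells nothing more about Week 12. Where those two values do not capture the device effect, imputed subjects in both arms are given a common response rate. The estimated difference is then pulled towards zero. The nested superiority test uses the same difference.

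Separately, a woman who stops at, say, Week 5 and attends her exit visit contributes that reading as observed Week 12 data. That assumes the exit reading represents her Week 12 status. No planned missing-data analysis relaxes this assumption, so the tipping-point grid can look more reassuring than the amount of early stopping warrants.

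**Working it through.** **1. The plan's own figure.** Inputs from SAP 1.4: 52% and 71%, margin 5 points, one-sided 0.025, power 90%. The distance to the margin is 0.71 − 0.52 + 0.05 = 0.24, and the average rate is 0.615. n = 2 × 0.615 × 0.385 × (1.960 + 1.282)² / 0.24² = 86.4, so 87 per group, as stated. No dropout rate is given. The steps below use 90 per arm.

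**2. Dilution from imputing without arm.** Assume a share m of each arm is imputed and, as the upper bound, baseline and Week 4 carry no arm information. Imputed subjects then respond at (71 + 52)/2 = 61.5% in both arms, and the expected difference is (1 − m) × 19:
- m = 10%: 0.9 × 19 = 17.1 points
- m = 20%: 0.8 × 19 = 15.2 points

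**3. Power.** Simulation (20,000 trials, ten imputations, Rubin's rules) at 71%/52%:

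| Imputed per arm | MI by arm | MI without arm |
|---|---|---|
| 10% | 88% | 85–86% |
| 20% | 84% | 76% |

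**4. Type I error at the margin (47%/52%).** The expected difference moves from −5 to −4.5 or −4.0, which by itself favours non-inferiority. The standard error works the other way. At m = 20% the true spread of the estimate is about 0.8 × √[(0.47 × 0.53 + 0.52 × 0.48)/72] = 6.7 points, before the small noise from using ten imputations. Rubin's rules start from about √[(0.2491 + 0.2496)/90] = 7.4 points and add between-imputation variance. The interval is therefore too wide. Simulated Type I error is about 1.7–1.9% (10% imputed) and about 1.2% (20%), against about 2.7% by arm.

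**5. Tipping-point grid and early-termination readings.** Assume every stopper returns outside the window and completers respond at the planning rates. Lower limit = d − 1.96 × √[pV(1 − pV)/90 + pC(1 − pC)/90]. As written, nobody is missing and the grid is a single cell. If these subjects are counted as missing instead:

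| Stoppers (Vital/itouch) | Cells | Worst lower limit | Cells at or below −5 |
|---|---|---|---|
| 4/4 | 25 | −0.8 | 0 |
| 9/9 | 100 | −6.5 | 3 |
| 9/18 | 190 | −10.8 | 20 |
| 18/9 | 190 | −14.5 | 45 |

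Example, 9/9: completer responders are 58 of 81 and 42 of 81. The worst cell is 58/90 against 51/90, so d = 7.8 and the lower limit is −6.5.

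**6. Is another primary rule better?** Let e be the share stopping early, and suppose exit response is half the arm's rate p while true Week 12 response equals p. The stored rate is p(1 − 0.5e). With e = 10% Vital and 20% itouch, 0.47 × 0.95 − 0.52 × 0.90 = −2.15 points. That is a shift of +2.85, and Type I error is 5.8%. With 20%/10% the shift is −2.10 and the error 1.2%. If instead the exit reading is the true Week 12 status, the SAP rule gives 2.7–2.8%, while imputing by arm gives 1.0% (10%/20%) and 4.9% (20%/10%). With equal early termination of 10% or 20%, either rule gives 2.3–3.0%.

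**The case against.** **The storage rule is a deliberate, pre-specified choice.** This stands. SAP 1.6.2 implements Protocol 8.11.1 and settles that the reading is observed. A reader might infer a conflict between the documents, or a gap over whether the reading counts. The text supports neither. Only the lack of a check remains.

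**The per-protocol analysis and other summaries cover early stoppers.** Partly. SAP 2.1 could exclude them through its compliance or protocol-deviation criteria, which are finalised before unblinding. SAP 2.2 tabulates completion status and reasons for discontinuation, and percent of target use would show short exposure. However, a stored exit reading meets the requirement for 12-week outcome data, no compliance threshold is given, and dropping subjects does not test what their Week 12 value would have been. LOCF gives no test either: if the Week 12 field were blanked, the most recent value would be the same exit reading.

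**The failing cells are extreme.** This stands. They need full off-window return; any stopper who does not return is already in the grid. In the 9/9 case all three failing cells have at most 1 of 9 Vital stoppers and at least 8 of 9 itouch stoppers responding. The 2:1 imbalances have no basis in the documents. Cell counts show how much the grid leaves out, and they do not measure bias.

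**Week 4 leakage is in the imputation model.** This also stands. It will carry some of the device effect, so the dilution figures are an upper bound.

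**Conclusion.** Both parts hold, as minor points.

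The imputation model omits the variable being compared. The cost is a difference biased towards zero and lost power: at most about 2 points and 2–3 percentage points of power with 10% imputed, or 4 points and 8 percentage points with 20%. This rests on planning rates, equal missingness and uninformative covariates. A reader might infer that shrinkage towards zero makes a false non-inferiority claim more likely. In the scenario examined it does not, because the overstated standard error outweighs the shift.

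The early-termination rule leaves an assumption untested. The effect is nil or slight at 4 to 9 stoppers per arm, and larger only with more or unequal early termination. A reader might infer that the primary rule should change. The calculations do not support that, since each rule misleads under some unequal pattern and the direction of any bias is unknown.

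The two sizes should not be added. A subject who returns for an exit visit is not imputed, so the same stoppers cannot produce both effects.

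A reader might also count the conditional modified ITT in SAP 2.1, which is missing from the change list in SAP section 4. It is disclosed where it is defined, and it should exclude few or no subjects because the first session is done in clinic. It is a documentation matter and forms no part of this point.

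**What to change.** 1. In SAP 2.3.2.1, run PROC MI by treatment arm, or add a treatment term to the imputation models. This is one line of code.
2. Keep the primary rule in SAP 1.6.2. Report, by arm, the number and study day of early-termination readings that fall outside Week 12 ± 7 days.
3. In SAP 2.3.2.2, add one sensitivity analysis that sets those readings to missing, imputes them by MI within arm, and counts those subjects in n1m and n2m of the tipping-point grid.

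The cost is a small SAP amendment, one extra table and a larger grid to present. The protocol, visit schedule and sample size do not change.

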1.6.3 CURRENT PROTOCOL

The current study protocol at the time of writing this SAP is version 2.0 FINAL 27MAR2015. Any future amendments to the protocol will be reviewed for their impact on this SAP, which will be updated only if necessary.

1.6.4 SOFTWARE

Analyses will be conducted using SAS for Windows version 9.3 or later. In the event that an analysis is required that is better suited for a statistical package other than SAS, another package (e.g. R) will be used.

2 ANALYSIS

2.1 ANALYSIS POPULATIONS

The primary analysis population will be the intent to treat (ITT) population. This will include all randomized subjects. Subjects will be summarized according to their randomized assignment. If there are randomized subjects who do not use the device at least once, a modified ITT (mITT) population will be defined to exclude such subjects and this population will be used in place of ITT.

A per-protocol (PP) population will also be evaluated for the primary endpoint. This population will consist of subjects who:

- Signed informed consent
- Met inclusion/exclusion criteria
- Were treated per randomized assignment
- Had 12 week outcome data available
- Met study compliance criteria
- No significant protocol deviations

Prior to locking the database, the PP criteria will be reviewed, additional criteria will be added if needed, and a listing of PP violations will be generated. The Sponsor/CRO will review this list and determine exclusions from this population. The final list of PP criteria and exclusions will be documented prior to unblinding.

The Safety population will include all randomized subjects who used the device at least once. Subjects will be summarized according to the actual device used, rather than the randomized assignment.

2.2 SUBJECT ACCOUNTING AND BASELINE CHARACTERISTICS

The ITT and PP populations will be summarized for the following demographic and baseline characteristics:

- age
- race and ethnicity

- menopause status
- height, weight, and BMI
- general medical history (ITT population only)
- physical examination findings (ITT population only)
- prior and concomitant medications (ITT population only)

Baseline assessments of stress urinary incontinence data will be summarized for the ITT and PP populations. Incontinence Quality of Life Questionnaire (I-QOL) scores and Pelvic Organ Prolapse/Urinary Incontinence Sexual Questionnaire (PISQ-IR) scores will be summarized for the ITT and PP populations. Study completion status and primary reason for discontinuation will be summarized for the ITT population. Medical history will be coded using Medical Dictionary for Regulatory Activities (MedDRA) and medications will be coded using the World Health Organization Drug dictionary (WHO Drug).

2.3 EFFICACY ENDPOINTS

2.3.1 PRIMARY ENDPOINT

The primary endpoint is defined as the proportion of subjects considered to have achieved ‘significant improvement’ following a provocative pad weight test at 12 weeks compared to baseline. ‘Significant improvement’ is defined as greater than 50% reduction in urine leakage from baseline.

2.3.2 PRIMARY ENDPOINT HYPOTHESIS

The primary hypothesis is that the proportion of subjects who respond (i.e. have achieved ‘significant improvement’) using Vital Compact is not less than 5% worse than the itouch Sure Pelvic Floor Exerciser (i.e. the lower bound of the confidence interval about the difference between device groups should be greater than -5%):

$$H_0: p_{Vital\ Compact} - p_{control} \leq -5\%$$

$$H_1: p_{Vital\ Compact} - p_{control} > -5\%$$

where $p_{Vital\ Compact}$ is the proportion of subjects who respond with Vital Compact and $p_{control}$ is the proportion of subjects who respond with itouch Sure Pelvic Floor Exerciser.

If the primary hypothesis of non-inferiority is met, a hierarchically-nested test of superiority will be performed. The hypothesis for the assessment of superiority is:

$$H_0: p_{Vital\ Compact} - p_{control} \leq 0\%$$

$$H_1: p_{Vital\ Compact} - p_{control} > 0\%$$

